#### 6.6.1.1. Scheduled Part A, First Cohort DMC Stopping Rule Assessment

Using the probability data presented in [Table 9](#) below, the likelihood of a Grade 3 VOE occurring in more than 2 of 4 subjects comprising the first Part A cohort within approximately one week would be 8.37%, assuming that the true incidence using plerixafor alone is 30%. Therefore, if more than 2 of the 4 subjects in the first Part A cohort report a Grade 3 VOE within approximately one week (up until the 1-week follow-up visit), no further dosing will take place unless the DMC determines that it is safe to do so.

**Table 9: Probabilities of Grade 3 VOEs Occurring in Given Numbers of Study Subjects Undergoing Apheresis in the First Patient Cohort of Part A Within Approximately One Week, if Mobilized with Plerixafor Alone**

Greater Than Grade 3 VOE	Probability if True=20%	Probability if True=30%	Probability if True=40%
$\geq 1/4$	59.04%	75.99%	87.04%
$\geq 2/4$	18.08%	34.83%	52.48%
$\geq 3/4$	2.72%	8.37%	17.92%
4	0.16%	0.81%	2.56%

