associated with severe sickle cell crises and death in patients with SCD or trait. Licensed in the US since 2008, plerixafor (Mozobil®, Genzyme) is a small molecule, reversible antagonist of chemokine receptor 4 (CXCR4), currently indicated to be used in combination with G-CSF to mobilize HSCs to the peripheral blood for collection and subsequent autologous transplantation in patients with multiple myeloma and non-Hodgkin's lymphoma. Plerixafor acts by disrupting binding to the receptor's cognate ligand, stromal-derived factor-1α (SDF-1α) chemokine ligand 12 (CXCL12), thereby resulting in mobilization of CD34+ HSCs into the peripheral blood. More recently, plerixafor alone has demonstrated efficacy in the mobilization of sufficient HSC for collection in patient populations, including SCD. However, as many as 75% of patients with SCD require 2 or more cycles of multi-day plerixafor administration and apheresis in order to collect sufficient HSCs for genetic modification and infusion, and vaso-occlusive crisis remains a risk with each mobilization and apheresis procedure, with approximately 30% of plerixafor-mobilized patients reported to have experienced VOEs of at least Grade 3 severity during and after harvesting, and approximately 20% of patients reported to have experienced serious vaso-occlusive pain within 2 days post-procedure. Hypomagnesemia, hypokalemia, and hypocalcemia have also been reported commonly among patients with SCD mobilized with plerixafor, although most events were Grade 1 or 2 in severity. Approximately half of patients with SCD require opioid medications within a week prior or subsequent to mobilization and apheresis. Nonetheless, mobilization with plerixafor seems to result in an apheresis product superior to bone marrow harvest, based on the concentration of high-quality CD34+ HSCs most suitable for *ex vivo* manipulation and autologous transplantation.

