## 6.6. Stopping Rules

### 6.6.1. Scheduled Stopping Rule Assessments

For the purposes of this study, a vaso-occlusive event (VOE, aka: vaso-occlusive crisis, sickle cell pain crisis) is defined as pain and/or injury as a result of ischemia due to vascular obstruction by sickled RBCs. Clinical manifestations of VOEs may include episodes of acute pain and/or evidence of organ involvement presenting as priapism, acute chest syndrome, splenic sequestration, hepatic sequestration, cerebrovascular ischemic event, or dactylitis.

Patients with SCD are known to commonly experience VOEs during and immediately following mobilization and apheresis, with approximately 30% of plerixafor-mobilized patients reported to have experienced a  $\geq$ Grade 3 VOE during and after apheresis, and approximately 20% of patients reported to have experienced serious vaso-occlusive pain within 2 days post-procedure. The stopping rules described below have therefore been designed to be triggered if the frequency of Grade 3 VOEs occurring within approximately one week (1-week follow-up visit, occurring 7 to 10 days) after MGTA-145 dosing exceeds that which would be expected using plerixafor alone, to be evaluated at each scheduled DMC assessment. Pain occurring during the infusion or immediately after infusion and resolving within 1 hour of infusion will not be considered a VOE and will not count toward the stopping rule. Furthermore, as described below in Section 6.6.1.3. (Unscheduled Stopping Rule Assessment), the occurrence of a  $\geq$ Grade 4 VOE in any subject occurring within approximately one week (1-week follow-up visit, occurring 7 to 10 days) after MGTA-145 dosing will be considered a stopping rule.

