### 6.6.1.2. Scheduled Part A, Second Cohort DMC Stopping Rule Assessment:

Based on the probability data presented in [Table 10](#) below, the likelihood of a Grade 3 VOE occurring in more than 3 of 7 subjects completing Part A within approximately one week would be 12.60%, assuming that the true incidence using plerixafor alone is 30%. Therefore, if more than 3 of 7 patients completing Part A at a specific dosing regimen report a Grade 3 VOE within approximately one week (up until the 1-week follow-up visit), the study will not progress to Part B dosing unless the DMC determines that it is safe to do so.

**Table 10: Probabilities of Grade 3 VOEs Occurring in Given Numbers of Study Subjects Undergoing Apheresis in the Second Patient Cohort of Part A Within Approximately One Week, if Mobilized with Plerixafor Alone**

Probability of $\geq$ Grade 3 VOE	Probability if True=20%	Probability if True=30%	Probability if True=40%
$\geq 1/7$	79.03%	91.76%	97.20%
$\geq 2/7$	42.33%	67.06%	84.14%
$\geq 3/7$	14.80%	35.29%	58.01%
$\geq 4/7$	3.33%	12.60%	28.98%
$>5/7$	0.47%	2.88%	9.63%
$>6/7$	0.04%	0.38%	1.88%
7	0.01%	0.02%	0.16%

Furthermore, the DMC may determine that the study should not proceed to the subsequent cohort at the current dosing regimen, based on the entirety of data available, regardless of whether a cohort stopping rule has been met.

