## 11. ASSESSMENT OF SAFETY

Subject safety will be assessed based on monitoring of AEs, vital signs, physical examinations, clinical laboratory evaluations, and development of anti-drug antibodies. Adverse events will be graded using the NCI CTCAE version 5.0.

Vaso-occlusive events are known to be associated with plerixafor use in patients with SCD undergoing mobilization and apheresis, reaching Grade 3 or higher severity in approximately 30% of patients. During each planned post-cohort assessment, the DMC is to evaluate and recommend whether to proceed to the subsequent cohort at the current dosing regimen based on evaluation of safety, PK, and mobilization kinetics. At each assessment, the number and proportion of patients reporting VOEs within approximately one week (1-week follow-up visit, occurring 7 to 10 days) after MGTA-145 dosing will be determined, and the DMC will determine whether a stopping rule has been met (Section 6.6), in which case no further dosing at that dosing regimen will take place unless the DMC determines that it is safe to do so. Pain occurring during the infusion or immediately after infusion and resolving within 1 hour of infusion will not be considered VOE and will not count toward the stopping rule.

In Part B, if a subject has a VOE following the first MGTA-145 infusion, proceeding to the second infusion will be at the Investigator's discretion.

As described below in Section 6.6, the occurrence of a Grade  $\geq 4$  VOE in any subject within approximately one week (1-week follow-up visit, occurring 7 to 10 days) after MGTA-145 dosing will be considered a stopping rule.

Excluding VOE, if any subject develops a Grade 3 or higher drug-related TEAE, based on the NCI CTCAE version 5.0, dosing of the current cohort will not be continued until the DMC assesses whether dosing may continue and whether dosing modifications are needed. In addition to VOEs, Grade 3 AEs known to be associated with plerixafor (i.e., nausea, vomiting, diarrhea, headache [as per plerixafor label]) or MGTA-145 (i.e., bone pain that is less than 1 hour in duration from the time the bone pain is first reported) will not count toward this stopping rule.

Pre-medications will be at the discretion of the Principal Investigator according to institutional or center standard for apheresis collection. All subjects will have adequate hydration before and during the apheresis procedure.

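### The scheduled VOE stopping rules count Grade 3 events, while the 30% reference and the printed trigger probabilities are for Grade 3 or higher

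*Protocol*

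**What the plan says.** **Reference rate.** The Introduction reports that about 30% of plerixafor-mobilized patients "experienced VOEs of at least Grade 3 severity during and after harvesting". Section 11 repeats the rate as "reaching Grade 3 or higher severity in approximately 30% of patients", and Section 6.6.1 also quotes it for Grade 3 or higher.

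**Rules.** Section 6.6.1 says the rules are "designed to be triggered if the frequency of Grade 3 VOEs occurring within approximately one week" exceeds what plerixafor alone would produce. Section 6.6.1.1 applies "if more than 2 of the 4 subjects in the first Part A cohort report a Grade 3 VOE within approximately one week", with the consequence that "no further dosing will take place unless the DMC determines that it is safe to do so". Section 6.6.1.2 bars progress to Part B, unless the DMC finds it safe, "if more than 3 of 7 patients completing Part A at a specific dosing regimen report a Grade 3 VOE". None of the three adds the words or higher.

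**Tables.** Both table titles speak of Grade 3 VOEs. The Table 9 header reads "Greater Than Grade 3 VOE", and the Table 10 header says Grade 3 or higher. The Table 9 title describes events "Occurring in Given Numbers of Study Subjects Undergoing Apheresis in the First Patient Cohort of Part A".

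**Separate rule.** Under Section 6.6.1.3, one VOE of Grade 4 or higher within about a week pauses dosing of the current cohort until the DMC has assessed it. This is in addition to the cohort rules.

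**The concern.** A stopping rule should count the event whose background rate was used to calibrate it. Here the rate covers Grade 3 or higher and the operative text covers Grade 3. The wording cannot safely be taken as loose shorthand, because Section 6.6.1.3 uses the threshold sign where a threshold is meant and sends Grade 4 and above to a rule of its own. Nothing says that such an event also counts toward 3 of 4 or 4 of 7. What is at stake is whether the formal rule is met at a look with only 4 or 7 subjects.

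Two related loose ends sit in the same text. The population counted is described in several ways, so it is unclear whether a dosed subject without a successful collection counts. Section 11 also restates the rules in terms that differ from Section 6.6.

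**Working it through.** **1. Reproduce the printed figures.** Exact binomial tail, P(X ≥ r) = Σ C(n,k) p^k (1−p)^(n−k) for k = r to n, with p = 0.30 from Section 6.6.1.

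- Look 1, n = 4, r = 3: 4 × 0.3³ × 0.7 + 0.3⁴ = 0.0756 + 0.0081 = 8.37%, as printed.
- Look 2, n = 7, r = 4: 35 × 0.3⁴ × 0.7³ + 21 × 0.3⁵ × 0.7² + 7 × 0.3⁶ × 0.7 + 0.3⁷ = 12.60%, as printed.

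There is no arithmetic error in these figures. They are correct for the event with the 30% rate, which is Grade 3 or higher.

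**2. Literal count.** The protocol does not split the 30% by grade, so the Grade ≥4 part is assumed. The DMC is also assumed to have cleared each such event under Section 6.6.1.3. The Grade 3 rate is then 30% minus that part.

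| Assumed Grade ≥4 part | Grade 3 rate | P(≥3 of 4) | P(≥4 of 7) |
|---|---|---|---|
| 0 points (intended event) | 30% | 8.37% | 12.60% |
| 1 point | 29% | 7.63% | 11.34% |
| 5 points | 25% | 5.08% | 7.06% |
| 10 points | 20% | 2.72% | 3.33% |

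The last row equals the printed 20% columns of Tables 9 and 10.

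**3. A concrete case.** Four subjects: two with Grade 3 VOEs, one with a Grade 4 VOE that the DMC has cleared, one without a VOE. Counting Grade 3 or higher gives 3 of 4, so the rule is met. Counting Grade 3 literally gives 2 of 4, so it is not.

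**4. Who is counted.**

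| Place | Population |
|---|---|
| 6.6.1.1 | the 4 subjects of the cohort |
| 6.6.1.2 | patients completing Part A at a given regimen |
| Table 9 and 10 titles | subjects undergoing apheresis |
| 8.1.1, 12.5 | 4 and 7 evaluable subjects |
| 11 | patients with VOEs after MGTA-145 dosing |
| 12.1, Safety Analysis Set | all enrolled and dosed |

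Evaluable means successful apheresis in Section 12.1, but absence of a major deviation affecting the primary endpoint in Section 12.5. Table 6, footnote b, foresees a dosed subject who does not complete apheresis and requires follow-up. Section 12.5 allows further enrolment to reach the evaluable minimum. No sentence says whether the first subject's VOE counts.

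If all dosed subjects count, the denominator may exceed 4 or 7 and a threshold is needed. Keeping 3 and 4 events with one extra subject at an ordinary 30% risk gives P(≥3 of 5) = 16.31% and P(≥4 of 8) = 19.41%.

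If instead the extra subject is there because a VOE prevented collection, one event is already in the count. Let q be the share of Grade ≥3 VOEs that prevent collection, assumed to be 5%, 10% or 25%. The rate among evaluable subjects is 0.3(1−q)/(1−0.3q) = 28.9%, 27.8% or 24.3%. The rule then needs 2 more of 4 (33%, 31%, 25%) or 3 more of 7 (33%, 30%, 23%). The threshold is therefore a real choice and does not follow automatically from the wording fix.

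**5. Section 11 against Section 6.6.**

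- Consequence of a met scheduled rule: Section 11 stops dosing at that regimen. Section 6.6.1.1 stops all further dosing and 6.6.1.2 stops progress to Part B.
- Exempt short-lived pain: bone pain in Section 11, musculoskeletal pain in 6.6.1.3.
- Drug-related Grade ≥3 TEAEs: no window in Section 11, about one week in 6.6.1.3.

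**The case against.** The best defence is that this is editorial. The Table 10 header and the stated source of the 30% make the intended event plain, and the printed probabilities are right. Any VOE of Grade 4 or higher reaches the DMC at once under the stricter rule in Section 6.6.1.3. The three-dose-stage review belongs to the same DMC throughout: it decides whether a rule is met (Section 11) and may refuse to proceed on the whole of the data regardless of the count (Section 6.6.1.2). In Section 11, the limit to one regimen can be squared with the regimen-specific count in 6.6.1.2 and the lower-dose option, and the missing window only makes that text more cautious. Most of this stands, and it limits the consequence. It does not remove the mismatch, because the rules are fixed in the protocol itself, whatever the DMC Charter (not shown) may add.

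Two stronger readings are tempting, and the documents do not support them.

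- A reader might infer that one miscounted subject switches the study from a default hold to a default to proceed. There is no default to proceed. The Synopsis and Section 6.3 require DMC evaluation before cohort 2 and again before Part B, whether or not a rule is met.
- A reader might infer that a dosed subject whose VOE prevents collection is replaced and dropped from the count. No text says so. In Section 12.5, replacement is for subjects discontinued before study drug. The evaluable numbers there can be read as the minimum for holding a look rather than as the list of who is counted, and a VOE is not in itself a protocol deviation. Section 11 and the Safety Analysis Set point to all dosed subjects. What remains is an ambiguity.

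**Conclusion.** The event is wrongly worded in Sections 6.6.1, 6.6.1.1 and 6.6.1.2, both table titles and the Table 9 header. This follows from the text alone and needs no assumption. The size depends on an unknown share of Grade ≥4 VOEs and on the DMC clearing them: over 1 to 10 assumed points, the probability of meeting the literal rule at the reference rate falls from 8.37% to between 7.63% and 2.72%, and from 12.60% to between 11.34% and 3.33%.

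The point is minor. It changes whether the formal rule is met, not whether dosing goes on unreviewed. The population counted is left open rather than wrongly fixed, and such cases are probably few: Section 10.2.2 caps collection at 8 hours, while the VOE window runs to the 7-to-10-day visit.

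**What to change.** - Write Grade 3 or higher in Sections 6.6.1, 6.6.1.1 and 6.6.1.2, in the titles of Tables 9 and 10, and in the Table 9 header. The cost is wording only; 8.37% and 12.60% stay as they are.
- State in Section 6.6 that the VOE count includes every subject dosed with MGTA-145, whether or not apheresis succeeded. The sponsor and DMC should choose and record the threshold for the case where more than 4 or 7 subjects have been dosed. Keeping 3 and 4 events means more frequent holds, as shown in the working, and the DMC can lift them.
- Align Section 11 with Section 6.6 on the consequence of a met rule, the exempt pain term (musculoskeletal pain under 1 hour) and the one-week window for drug-related Grade ≥3 TEAEs.

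The planned numbers of evaluable subjects do not change.

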### 6.6.1.2. Scheduled Part A, Second Cohort DMC Stopping Rule Assessment:

Based on the probability data presented in [Table 10](#) below, the likelihood of a Grade 3 VOE occurring in more than 3 of 7 subjects completing Part A within approximately one week would be 12.60%, assuming that the true incidence using plerixafor alone is 30%. Therefore, if more than 3 of 7 patients completing Part A at a specific dosing regimen report a Grade 3 VOE within approximately one week (up until the 1-week follow-up visit), the study will not progress to Part B dosing unless the DMC determines that it is safe to do so.

**Table 10: Probabilities of Grade 3 VOEs Occurring in Given Numbers of Study Subjects Undergoing Apheresis in the Second Patient Cohort of Part A Within Approximately One Week, if Mobilized with Plerixafor Alone**

Probability of $\geq$ Grade 3 VOE	Probability if True=20%	Probability if True=30%	Probability if True=40%
$\geq 1/7$	79.03%	91.76%	97.20%
$\geq 2/7$	42.33%	67.06%	84.14%
$\geq 3/7$	14.80%	35.29%	58.01%
$\geq 4/7$	3.33%	12.60%	28.98%
$>5/7$	0.47%	2.88%	9.63%
$>6/7$	0.04%	0.38%	1.88%
7	0.01%	0.02%	0.16%

Furthermore, the DMC may determine that the study should not proceed to the subsequent cohort at the current dosing regimen, based on the entirety of data available, regardless of whether a cohort stopping rule has been met.

### 6.6.1.3. Unscheduled Stopping Rule Assessment

In addition to the cohort stopping rules outlined above, if within approximately one week (up until the 1-week follow-up visit) after MGTA-145 dosing, any subject develops a Grade  $\geq 4$  VOE, or a Grade  $\geq 3$  drug-related TEAE (based on the National Cancer Institute (NCI) Common Terminology Criteria for Adverse Events (CTCAE) version 5.0) other than VOE, dosing of the current cohort will not be continued until the DMC assesses whether dosing may continue and whether dosing modifications are needed. In addition to VOEs, Grade 3 AEs known to be associated with plerixafor (i.e., nausea, vomiting, diarrhea, headache [as per plerixafor label]) or MGTA-145 (i.e., musculoskeletal pain that is less than 1 hour in duration from the time pain is first reported) will not count toward this stopping rule.

## 6.7. Criteria for Study Stopping/Termination

The Sponsor (Magenta) may stop/terminate the study due to the following reasons:

- Emergence of unacceptable safety risk to subjects.
- Failure of the Investigator or site to adhere to the protocol or regulatory requirements.

If the Sponsor decides to stop/terminate the study, the Sponsor will promptly notify the Principal Investigator and the relevant regulatory authority. The Principal Investigator will be responsible for notification of the Institutional Review Board (IRB)/Independent Ethics Committee (IEC).

## 7. SELECTION AND WITHDRAWAL OF SUBJECTS

### 7.1. Criteria for Inclusion for Parts A and B

1. Subject must be 18 to 35 years of age, inclusive.
2. Subject must weigh  $\geq 30$  kg at screening.
3. Subject must have a documented diagnosis of SCD, with documentation of SCD genotype by medical history.
4. Subject must present with a feasible manual or automated exchange transfusion plan to achieve Hemoglobin S (HbS)  $<30\%$  within 1 week of mobilization.
5. Subject taking hydroxyurea must comply with a washout period of at least 30 days prior to mobilization dosing. Subjects must be able to safely discontinue hydroxyurea to participate in the study.
6. Subject must have a local laboratory screening white blood cell (WBC) count  $>2.0 \times 10^9/L$ , absolute neutrophil count (ANC)  $>1.0 \times 10^9/L$ , and platelet count  $>150 \times 10^9/L$
7. Subject must have a local laboratory screening estimated glomerular filtration rate (eGFR) of at least 60 mL/min/1.73 m^2 based on the CKD-Epi equation.
8. Subject must have a local laboratory screening alanine aminotransferase (ALT) value  $<2.5 \times$  upper limit of normal (ULN).
9. Subject's cardiac and pulmonary status must be sufficient to undergo apheresis, as assessed by the Investigator.
10. Subject must sign an IRB-approved informed consent form (ICF) and be willing to comply with the requirements of the protocol.

### 7.2. Criteria for Exclusion for Parts A and B

1. Subject with a VOE requiring a visit to a healthcare facility within 30 days of screening.
2. Subject with onset of clinically apparent cerebrovascular accident (CVA) or retinal infarct in the 2 years prior to screening or determined to be at high risk of CVA, based on concomitant disease (e.g., moyamoya), or imaging (e.g., trans-cranial doppler study).
3. Subject with splenomegaly, splenic sequestration, sickle hepatopathy, priapism requiring inpatient treatment, acute chest syndrome requiring supplemental oxygen, or osteomyelitis within 6 months of screening. Subjects with a history of splenomegaly or splenic sequestration may be included if they have undergone a splenectomy.
4. Subject having surgery requiring greater than local anesthesia within 3 months of screening, except for placement of a central venous access device.
5. Subject who has received or plans to receive anticoagulation at the time of screening, except for study-related procedures.

6. Subject who, by medical history, requires rare donor registry red blood cell (RBC) units for transfusion, or is unable to receive routine transfusion. Eligible study subjects must have undergone prior work-up for the presence of red cell alloantibodies and confirmation of available compatible blood product support.
7. Subject who has undergone or attempted and failed previous HSC collection.
8. Subject who has had a prior autologous or allogeneic transplantation, inclusive of gene therapy.
9. Subject who has received experimental therapy within 4 weeks of providing informed consent or is enrolled in another interventional experimental protocol.
10. Subject with poorly controlled diabetes mellitus, as assessed by the Investigator.
11. Subject who has an uncontrolled cardiovascular condition, including clinically significant cardiac arrhythmia, congestive heart failure, angina, myocardial infarction, or unstable pulmonary arterial hypertension within 6 months of screening.
12. Subject with a history of or who has a positive screening laboratory test for human immunodeficiency disease (HIV), hepatitis B, hepatitis C, or human T-cell leukemia virus (HTLV).
13. Subject with active infection or co-morbid condition that places the subject at high risk for treatment complications, as assessed by the Investigator.
14. Subject with a known allergy to or contraindication for MGTA-145, plerixafor administration, or medications routinely administered during apheresis.
15. Male subject not willing or able to use a highly effective method of contraception for 3 months during and after treatment with MGTA-145 and plerixafor, or female subject who is pregnant or breastfeeding, or sexually active and not willing or able to use a highly effective method of contraception for 3 months during and after treatment with MGTA-145 and plerixafor.

